#### BACKGROUND&RATIONALE

The past five years have increased the pace of progress towards controlling the HIV epidemic and reducing the number of new perinatal and sexually transmitted infections occurring each year. The major reason is effective treatment and prevention through antiretrovirals – used by HIV-positive individuals to treat HIV infection (ART) and prophylactically by HIV-negative individuals to prevent HIV infection (PrEP). However, much work remains to optimize ART and PrEP delivery to millions of people with and at high risk of HIV using strategies that will achieve the greatest effectiveness and coverage possible [3]. Uganda carries the fifth highest HIV burden in the world, with 1.6 million people living with HIV, and 140,000 new infections and 63,000 AIDS-related deaths in 2013 [4]. Uganda also has a high fertility rate (5.8 pregnancies per woman in 2015). A key driver of HIV incidence in Uganda is low utilization of antenatal and delivery services [5]. HIV-positive women are more likely to complete the PMTCT cascade when male partners are tested and engaged in care [6]. To have a greater impact of PMTCT B+ on HIV trends in Uganda in the context of a high fertility rate, it is critical to increase male HIV testing and uptake of PrEP or ART and women's post-partum ART continuation.

#### PMTCT B+ and the need for higher rates of ART use and adherence post-partum

Although there has been substantial progress in implementation of PMTCT B+, several challenges remain and need to be addressed, including post-partum ART continuation and adherence. These gaps and needs are highlighted by recent analyses from the PROMISE study, which was conducted in 52 clinical research sites in eight countries. The PROMISE study showed low acceptance of early ART among postpartum women globally (PROMISE studies 1077 BF/FF/HS). Women in PROMISE were informed of the benefits of early ART from the landmark START trial [7], but 33% did not accept early ART, citing concerns of i) wanting more time to consider ART and ii) stating she feels well [8]. Thus, despite intense ART education and HIV monitoring in a well-resourced clinical trial setting, one-third of women required additional counseling to start ART earlier for their own health.

The PROMISE study also included a randomized comparison of stopping or continuing ART in 1653 postpartum non-breastfeeding women with pre-ART CD4>400 cells/mm^3 (PROMISE study 1077HS). This study demonstrated clinical benefits of post-partum ART; women who were randomized to continue ART had a 32% lower risk of reaching the primary endpoint of time to an AIDS event, and a 44% lower risk of reaching an AIDS event or a WHO stage 2 or 3 event [9]. Importantly, among women randomized to continue ART, 23% had virologic failure; 86% of women with viremia did not have genotypic resistance, indicating non-adherence as the likely cause of their viremia[9]. Interventions to improve adherence are needed to achieve long-term benefits in post-partum women on ART.

In contrast, in our recently completed demonstration project of integrated PrEP and ART delivery with 1013 high-risk HIV serodiscordant couples in Kenya and Uganda, the rate of viral suppression at 12 months was higher in women who initiated ART during pregnancy than for other indications (96% vs 87%, p=0.02) [10]. This finding merits further study for integrated PrEP and ART delivery in PMTCT B+ programs to improve effective ART use post-partum, when coupled with safe, acceptable, and effective strategies to increase HIV testing in male partners of unknown status, and to motivate male partners who test to use of PrEP or ART, based on their sero status and with effective linkage strategies.

#### Low uptake of HIV testing by male partners: A barrier to PMTCT B+ success

HIV testing is consistently lower among African men than women, leading to a higher proportion of undiagnosed HIV infection among men [11, 12]. Women who learn they are HIV-positive, often in antenatal care, are sometimes unwilling to disclose their HIV status due to fear of domestic violence, stigmatization or divorce [13]. Safe and acceptable solutions to this challenge need to be identified in order to optimize the benefits of PMTCT for mothers and infants; past research has shown that HIV-positive women are more likely to complete the PMTCT cascade when their male partners are tested and engaged in care [6]. Male partner involvement increases condom use [14, 15], women's utilization of antenatal services and HIV testing [16-18], obtaining HIV results [19], ART use [14, 19, 20], adherence to infant feeding advice [21-24], infant HIV testing [25], and infant HIV-free survival [25, 26]. Despite these multiple benefits, studies from Africa have found that male partner testing rates remain low (16-54%) [14, 20, 27, 28]. Barriers to male partner involvement include fear of knowing one's status, stigma [28, 29], men's belief that their status is the same as their partners (i.e., testing by 'proxy') [23], cultural norms that men should not accompany their wives to antenatal care [13], negative attitudes of health care workers [30, 31] (i.e., not allowing men in antenatal clinics) [29, 30, 32], and men's concern about time away from work and the impact on their income [29, 31-34].

#### Health system facilitators of male engagement in PMTCT

Multiple interventions have tried to increase male involvement in PMTCT programs, including the provision of personalized invitation letters to men whose female partners have engaged with the program. Men often perceive invitation letters as a medical prescription, which increases their sense of obligation to attend [13]. However, partner return following receipt of official invitation letters is not high –36% in Kenya [35], 26-35% in South Africa [36], 28% in Malawi [37] and 16% in Uganda [38]. Couples HIV testing and counseling improves uptake of HIV testing and ART without increased risk of social harm, compared with individual counseling [14, 39]. Other approaches include offering ANC services for couples during weekends or non-working hours [13] and intra-partum HIV testing and counseling [40]. Couples testing, flexible hours, expedited clinic processing for women who bring male partners [40], male support groups [31] and peer sensitization of men [29]modestly increased male partner involvement in some PMTCT programs, but have not achieved substantially large increases in partner testing.

#### Self-testing kits as innovation in HIV testing of male partners of pregnant HIV-positive women

HIVST is a highly acceptable and innovative approach to increasing knowledge of HIV sero status among many populations that have limited access to or low uptake of HIV testing services [41-43]. Studies conducted in high- and low-income settings have shown that self-tests can be used accurately by lay users [44], and that they overcome various barriers to facility-based testing [41]. 45]. Self-tests offer a low-cost way to increase access to testing among hard to reach persons such as male partners of pregnant women. This potential was demonstrated by our colleague, [name], in a pilot of HIVST which offered multiple self-tests to HIV-negative women in antenatal and postpartum care in Kisumu, Kenya. Women were shown how to correctly use oral fluid-based self-tests, given three test kits with written and pictorial instructions, to distribute or use the tests with their male partner, based entirely on their discretion. Notably, over 90% of women distributed HIVST kits to their partners, and reported safer sexual decisions and rare social harms [46]. Acceptability indicators were very high; women reported HIVST kits were easy to use and their partners welcomed the opportunity to learn their HIV status conveniently and privately. To further evaluate this approach. [name] conducted a RCT of distribution of HIVST by pregnant and postpartum women to promote male partner and couples testing through antenatal clinics in Kisumu, Kenya [47]. Women in the intervention group received 2 oral fluidbased HIVST, while those in the comparison group were given referral vouchers that invited their

partner for HIV testing at clinics, alone or as a couple. The primary outcome was whether their partner had sought HIV testing in the past 3 months. Significantly higher rates of male partner testing were achieved in the HIVST arm (91% compared to 51% in the control arm), and couples testing increased by 42% and disclosure by 39% [47].

In the context of PMTCT B+ programs, HIVST is a promising approach to increasing male partner and couples testing, which has not yet been evaluated. The Kenyan pilot of secondary distribution of HIVST to male partners of pregnant women had encouraging results; however, only a minority (4%) of the 600 women enrolled were HIV-positive and thus more information is needed about how to tailor this approach to HIV-infected women in PMTCT programs. Specific aspects that need to be better understood are HIV-positive pregnant women's willingness and ability to motivate their male partner to test, which may differ from HIV-negative pregnant women, as well as social harms which may be more likely when male partners learn that their partner is HIVpositive. The importance of evaluating HIVST for male partners of women in PMTCT is that their male partners will either be HIV-negative (and thus in an HIV serodiscordant partnership where they could benefit from PrEP or voluntary medical male circumcision) or HIV-positive and need linkage to HIV care and ART. In summary, the feasibility and impact of secondary distribution of HIVST need to be evaluated in PMTCT B+ programs with the expectation that HIV-positive women will require additional counseling and support to broach HIVST with their partners.

#### PMTCT B+ in Uganda

Since PMTCT B+ became Ugandan national policy in late 2012, 94% of HIV positive pregnant women receive ART to reduce risk of mother-to-child transmission. Retention of women 6 months after ART initiation during pregnancy was 88%[48], and 90% on ART had undetectable viral load after >6 months of ART. While progress is being made in ART uptake among pregnant women in PMTCT B+ programs in Uganda, male engagement remains low (23%)[5].Mulago Hospital is the main referral hospital in Uganda, where ~23,000 pregnant women attended antenatal clinics in 2015, 85% received an HIV test, and 3.3% were HIV positive with an average of 54 women initiating ART per month in PMTCT B+. Male partner involvement strategies at Mulago include invitation letters and phone calls to encourage HIV testing and assist with disclosure. Their experience with these strategies is mixed, as many invitation letters were not delivered. However, when letters were delivered, men showed up, eager to find out why the doctor wanted to see them. Partners who came to clinic were given priority and seen quickly, to boost retention, since the main complaint of men is the time to attend clinic. In the Mulago PMTCT program, however, only 19% of male partners were tested. Retention in care 12 months after ART initiation was only 60% in 2015.

Offering HIVST to women and facilitating men's access to services are potential innovations to improve male partner testing and PMTCT outcomes. In Uganda, HIVST is currently limited to research studies. The Ugandan Ministry of Health (MoH) and Minister of Science, Technology and Innovation have expressed interest in HIVST projects, including this project which could improve PMTCT B+ outcomes.

#### Antiretrovirals to reduce HIV infectiousness and acquisition

The source of up to half of all new HIV infections in Africa is estimated to be among HIV serodiscordant couples – in which one partner is HIV-positive and the other is HIV-negative – a priority target population for HIV prevention interventions [49, 50]. Based on our experience in testing thousands of couples in East and southern Africa in past research studies, approximately half of male partners of HIV-positive women are expected to test HIV-negative and be in an HIV

serodiscordant partnership and half to test HIV-positive [51].

Following diagnosis of HIV serodiscordancy, couples face challenges as they strive to preserve their relationship and keep the HIV-negative partner uninfected amidst desires for intimate sex and safe pregnancy [52, 53], PrEP for the HIV-negative partner and ART for the HIV-positive partner can provide high levels of protection and a long-term solution for HIV serodiscordant couples [54, 55].

ART use by HIV-positive persons, with high adherence and maintenance of viral suppression, is the ultimate goal for long-term prevention of HIV transmission within HIV serodiscordant couples [7, 56]. The time between ART initiation and viral suppression (up to 6 months) [57], and common delays in ART initiation [58] are the period of highest HIV risk for HIV-negative partners. During this period PrEP can provides near complete protection to an HIV-negative person – the basis of an integrated PrEP and ART strategy [59]. Multiple randomized trials among different at-risk populations have demonstrated high efficacy of tenofovir-based PrEP [60-63].

The 2015 WHO guidelines recommend PrEP for people with substantial HIV risk, operationalized as populations with  $\geq$ 3% annual HIV incidence, including HIV serodiscordant couples [64]. With release of WHO guidelines, there is growing enthusiasm for PrEP implementation in resource-limited settings; Kenyan and South African drug authorities rapidly approved PrEP in 2015 [64, 65]. Implementation plans have been developed in Kenya, South Africa, and are being developed in Uganda and other African countries. The focus for PrEP implementation is on innovative approaches to PrEP delivery for high-risk populations, such as HIV-negative male partners of women in PMTCT B+ programs. These implementation strategies require evaluating men's willingness to be tested through innovative methods, their PrEP uptake, and women's post-partum ART use and adherence.

#### PrEP as an effective bridge to ART and viral suppression

We tested the effectiveness of an integrated PrEP and ART strategy in our recently-completed

Partners Demonstration Project among 1,013 ARV-naïve HIV serodiscordant couples at 4 sites in Uganda and Kenya, including IDI Kasangati in Kampala (NIMH R01 MH095507, Bill & Melinda Gates Foundation OPP1056051, USAID AID-OAA-A-12-00023)[59]. In this model, PrEP provides protection against HIV acquisition prior to viral suppression in the HIVpositive partner (Figure 1, Scenario 1). For couples in which the positive partner does not initiate ART immediately upon diagnosis, the period of HIV risk is extended, and PrEP is used for a longer period of time (Figure 1, Scenario 2). We recruited couples with a predicted HIV incidence of ≥3% [66], who would most benefit from PrEP as a bridge to ART.

Overall, 97% of HIV-negative partners in the Partners Demonstration Project initiated PrEP and had high adherence with tenofovir detected in 82% of plasma samples. Similarly, we observed

high uptake and adherence to ART among HIV-infected partners; 91% initiated ART by 24 months with >90% viral suppression [59]. The integrated PrEP and ART strategy accelerates ART initiation; 90% of HIV-positive partners initiated ART within six months, compared to 50% in the Partners PrEP Study [58]. This integrated PrEP and ART strategy nearly eliminated HIV transmission with 95% reduction in HIV transmission (Figure 2); observed infections were compared to a counterfactual simulation model, bootstrapping data from the placebo arm of Partners PrEP, and sampling for the subset with a matching distribution of risk scores and follow-up [59]. High protection was observed among HIV-negative men (95% HIV reduction, p<0.0001), relevant to this project [67]. We found PrEP until the HIV-positive partner initiated ART was highly

acceptable, safe and effective [1, 2]. Thus, the Partners Demonstration Project provided strong evidence of high adherence and effectiveness of time-limited PrEP among HIV serodiscordant couples who were counseled about their risk of HIV exposure, who were young and many wanted children, and were counseled about the efficacy of PrEP and ART. These findings provided critical data for PrEP guidelines by WHO [64, 68], Kenya [65], and Ugandan guidelines, which are in development.

Relevant to this project, we also evaluated the feasibility and acceptability of HIVST among HIVnegative persons on PrEP in a sub study of the Partners Demonstration Project. Specifically, we evaluated HIVST in Thika, Kenya, in which HIV-negative partners on PrEP were provided two oral HIVST kits to use monthly between their quarterly visits. We found very high acceptability, with 99% of users reporting that HIVST kits were easy to use, empowering, and reduced anxiety between quarterly clinic-based HIV testing [69].

#### COVID-19 impact

The COVID-19 pandemic entered Uganda in March 2019 and Uganda's public health response implemented safety protocols such as shelter-in-place and transport restrictions, shortly after the first cases were confirmed. The impact of COVID-19 has disproportionately affected vulnerable populations, particularly pregnant women living with HIV, who face challenges in disclosure of their HIV status to their partners due to fear of loss of the partnership, economic support, and gender-based violence (GBV). This study will provide the opportunity to gather behavioral data on women's experiences with ART adherence, status disclosure and additional challenges faced during prepartum and postpartum, during the COVID-19 pandemic.

#### Summary

This project will address key challenges in PMTCT B+ programs, by evaluating innovative strategies to increase male partner testing through secondary distribution of HIVST by the female partners to overcome men's reluctance to test involvement in PMTCT. Confirmatory testing needs to follow with HIVST, and in the context of testing male partners of women in PMTCT B+, men who test will either learn that they are HIV negative and thus in an HIV serodiscordant partnership or HIV-positive. Thus, the linkages to HIV prevention and care are critical, and we will couple HIV testing with offering PrEP to HIV-negative men and ART to HIV-positive men and encouraging post-partum ART continuation and adherence among HIV-positive women.

#### STUDY METHODS

#### Overall design

This is a randomized trial of HIV-positive pregnant women and their partners. The overall goal is to evaluate the impact of innovative strategies on male partner HIV testing, and engagement in HIV care and prevention among men, on post-partum ART continuation and adherence among HIV-positive women. We will recruit HIV-positive women in PMTCT B+ programs in Kampala to be randomized to: 1) the intervention arm in which they receive HIVST kits for their partners with self-instruction materials about HIVST, encouragement to seek confirmatory testing and counseling along with a voucher and referral, and brief educational materials about PrEP and ART, or 2) the control arm in which they receive invitation letters to deliver to their partners that invite men to fast-track HIV testing at the clinic, along with brief educational materials about PrEP and ART. Women in the intervention arm will be instructed in the use and interpretation of HIVST and be provided two HIVST kits to give to or use with their male partners. Male partners will receive an educational brochure outlining the benefits of HIV testing and ART or PrEP. We will receive an educational brochure outlining the benefits of HIV testing and ART or PrEP. We will recommend that HIV-negative men use PrEP until their partner has achieved viral suppression, and that HIV-positive men take ART.

The co-primary outcomes of the study are the proportion of male partners who test and the proportion of HIV-negative male partners who take PrEP. The primary analysis is an intent to treat comparison by randomization arm of the primary outcome: proportion of women whose male partners who test HIV-uninfected and initiate PrEP within six months after their HIV-positive partner is randomized. A secondary outcome is an objective marker of PrEP adherence - tenofovir detection at 3 and 6 months - among men who initiate PrEP.

The secondary outcome is the proportion of HIV-infected women who are virally suppressed at 12 months post-partum, as the measure of continuation of ART and high adherence post-partum. We will also conduct observational analyses using marginal structural models to assess whether the HIV-positive woman's viral load at 12 months post-partum is improved by male partner testing and engagement in HIV care or prevention (PrEP use among HIV-negative men or ART use among HIV-positive men). Quantitative and qualitative methods will be used to assess acceptability of HIVST in PMTCT, PrEP among male partners who test negative, and identify ways to minimize social harms.

#### Objectives

# Aim 1: Determine whether an enhanced PMTCT program with HIV self-testing for male partners and provision of PrEP to HIV-negative male partners increases the proportion of male partners who test for HIV and men who initiate PrEP.

Innovations are needed to reach male partners for HIV testing that allow men to test where they are comfortable, which typically is not in busy antenatal clinics. Provision of HIV self-tests (HIVST) to pregnant women for their partners is safe, acceptable, and effective, and could facilitate partner testing, and increase uptake of PrEP by HIV-negative men and ART by HIV-positive men. HIVST is a promising approach to increasing partner and couples testing, which has not yet been evaluated in the

context of PMTCT B+ programs. We will randomize 500 HIV-positive women initiating PMTCT B+ in Kampala in a 2:1 ratio to one of two partner testing strategies: 1) HIVST kits (intervention) to give to or use with their partner, or 2) invitation letters for fast-track testing at the clinic (standard of care). Men who test will be offered confirmatory testing and counseling. Men who test HIV-positive will be linked to ART, and men who test HIV-negative will be offered PrEP for the first six months after his partner initiates ART through PMTCT.

The co-primary outcomes are the proportion of male partners who test for HIV and the proportion of HIV-negative men who initiate PrEP. The secondary outcome for this Aim is tenofovir detection at 3 and 6 months among men who use PrEP.

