## Table 3. Sample size calculations for comparison of proportion of

Randomization is 2:1 for Enhanced: SOC. Assumes 95% retention, 80% PrEP uptake

Assuming PrEP uptake in HIV-negative men is 80% and 60% of the men are HIV-uninfected, with a sample size of 500 we would have almost 90% power to detect an increase in PrEP use resulting from a change from 30% to 55% in test uptake. With 500 women, the power for assessing an increase in HIV test uptake exceeds 95% across a range of assumptions in Table 3.

Aim 2: Under the range of assumptions for HIV testing uptake in Aim 1, the overall HIV test uptake will be in the range 43-53% (Table 4) and the number of enrolled women with partners who test and begin ART or PrEP ranges from ~150-200. Assuming power for the causal inference can be approximated by logistic regression, we would have ~80% power to detect an OR of 1.75 or higher, assuming women have 50% ART continuation and viral suppression when male partners do not initiate PrEP or ART. If the number of women with partners who test is between 220-270, we would have approximately 85% power to detect an OR of 1.75.

Table 4. Power approximation for assessing impact of partner PrEP/ART use on women's viral suppression					
Overall HIV	HIV prevalence	HIV+ men on ART	Not on ART		

Overall HIV	HIV prevalence	HIV+ men on ART	Not on ART		
test uptake	in male partners	or HIV- men on	or PrEP		
		PrEP		OR=1.75	OR=2.0
43%	0.4	147	353	78%	92%
47%	0.3	166	334	81%	94%
50%	0.4	170	330	80%	94%
53%	0.3	189	311	83%	95%
Randomizatio	on is 2:1 for Enhance	ed: SOC. Assumes 95	% retention, 80	% PrEP upta	ke and

50% ART persistence

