3.4. Assessments

3.4.1. Male visit schedule:

Every three months after enrollment up to 12 month post-partum. Men will undergo informed consent for HIV testing and referral for HIV care and ART if they test HIV-positive, or offered PrEP if they test HIV-negative.

3.4.2. Pregnant women schedule:

Antenatal visit schedule to align with the PMTCT schedule. One visit expected every trimester. Study visits occur every three months after birth (post partum). Viral load (VL) monitoring will include plasma HIV RNA levels at enrollment, 6 and 12 months post-partum.

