7. ANALYSES

7.1. General Considerations

Inferential statistical tests will be two-sided and will be performed at alpha levels of 0.05 and 0.10 to declare the significance of main effects and interaction effects, respectively.

No adjustment for multiplicity are planned.

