7.2. Statement of the Null and Alternate Hypotheses

The null and alternative hypotheses are:

H_0 : Provision of self-test kits to the male partner by his pregnant partner does not have a differential effect on 1) male partner testing, 2) PrEP uptake in HIV-uninfected male partners or 3) viral suppression at 12 months in the women, compared to the standard of care (letter).

H_A : Provision of self-test kits to the male partner increases 1) male partner testing, 2) PrEP uptake in HIV-uninfected male partners and 3) viral suppression at 12 months in the women, compared to the standard of care (letter).

Subgroup Analyses

Subgroups of interest:

30 Sep 2021

- Women who have disclosed their HIV-infected status prior to/reported at baseline
- Women who were virally suppressed (VL < 50 copies/mL) at baseline
- Women <=24 vs > 24 years old
- Women who were on ARVs prior to their pregnancy

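### The documents disagree on which HIV-negative men may be offered PrEP and on the PrEP outcome window, and the power calculation has no term for men who cannot be offered it

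*Protocol*

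**What the plan says.** **Who is offered PrEP.** The documents give five rules.

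- Six months counted from the woman's ART start: Specific Aims and Objectives, Aim 1 ("men who test HIV-negative will be offered PrEP for the first six months after his partner initiates ART through PMTCT"), and the Benefits section of the protocol, which ends free access at that point.
- Any man who tests negative, with no time limit in the sentence: the opening paragraph on the trial in the protocol Summary, Male partner procedures, and SAP 3.4.1 ("or offered PrEP if they test HIV-negative").
- Until the woman is virally suppressed: protocol, Overall design.
- Six months *or* viral suppression: protocol, PrEP medication and dispensation.
- Six months *and* viral suppression: SAP Protocol Summary, Methodology.

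The Approach paragraph of the protocol Summary also covers the time before the woman starts ART. Protocol Table 6 lists PrEP provision at months 9 and 12 as indicated, without a rule.

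**When the PrEP outcome is counted.** Overall design and Statistical considerations count from randomisation, for six months. Outcome measurements counts to six months after the woman's ART start. SAP 7.3.3 tests initiation by end of study in enrolled men, and elsewhere in the same section refers to six months.

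**Who is recruited.** Aim 1 says "We will randomize 500 HIV-positive women initiating PMTCT B+ in Kampala in a 2:1 ratio". The eligibility list has no criterion on ART history. SAP 5.2.1 lists ART use at enrolment as a baseline variable, and SAP 7.2 plans a subgroup: "Women who were on ARVs prior to their pregnancy".

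**Power.** Protocol, Sample size, Aim 1: "Assuming PrEP uptake in HIV-negative men is 80% and 60% of the men are HIV-uninfected", with 500 women "we would have almost 90% power to detect an increase in PrEP use resulting from a change from 30% to 55% in test uptake". The note to Table 3 reads "Randomization is 2:1 for Enhanced: SOC. Assumes 95% retention, 80% PrEP uptake".

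**The concern.** Starting PrEP is a co-primary outcome, and a man who is not offered PrEP cannot have it. If a clinic follows the wording tied to six months from ART start, an HIV-negative man whose partner has been on ART for longer when he tests would not be offered PrEP. If it follows the unrestricted wording, he would be. Under either he counts as a non-initiator if he does not start.

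The outcome window raises the same problem separately. For a woman already on ART for more than six months at randomisation, the window in Outcome measurements closed before she entered the trial, so her partner cannot have that event whatever he is offered.

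Two things are at stake. First, if men who cannot start PrEP are spread evenly over the arms, both PrEP proportions shrink by the same factor, and the absolute difference and the power shrink with them. Second, without a record of the offer, a low PrEP proportion could be read as men declining PrEP when some were never offered it.

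**Working it through.** **Step 1: reproduce the stated power.** Inputs from protocol Table 3, its note and the sentence below it: test uptake 30% (standard of care) and 55% (HIVST), 60% HIV-negative, 80% PrEP uptake, 2:1 allocation, 95% retention, 500 women. The protocol gives no alpha; SAP 7.1 says "Inferential statistical tests will be two-sided and will be performed at alpha levels of 0.05 and 0.10", the first for main effects, so 0.05 two-sided is used.

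Event rates among all women: p1 = 0.30 × 0.6 × 0.8 = 0.144; p2 = 0.55 × 0.6 × 0.8 = 0.264.

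Sample size with unpooled variance: N = 3 × (1.960 + z)² × [p1(1−p1) + p2(1−p2)/2] / (p2−p1)² / 0.95.

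For 90% power (z = 1.2816): 3 × 10.507 × (0.12326 + 0.09715) / 0.0144 / 0.95 = 507.9. The table says 508. For 80% power the result is 379.4; the table says 379. All 16 cells of Table 3 agree to rounding.

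Power at 500 randomised: 475 retained, split 158.3 and 316.7. SE = √(0.12326/158.3 + 0.19430/316.7) = 0.0373. Then 0.120/0.0373 − 1.960 = 1.256, which gives **89.5%**. The stated figure is reproduced.

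**Step 2: add the missing term.** Let g be the share of HIV-negative testers who can be offered PrEP. The documents do not give it. It is an assumption here, taken as equal in both arms, with men outside it counted as non-initiators. Both event rates are multiplied by g.

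| Assumed g | p1 | p2 | Power, 475 retained | N for 90% power |
|---|---|---|---|---|
| 100% | 0.144 | 0.264 | 89.5% | 508 |
| 90% | 0.130 | 0.238 | 85.4% | 579 |
| 80% | 0.115 | 0.211 | 80.1% | 667 |
| 70% | 0.101 | 0.185 | 73.7% | 780 |
| 60% | 0.086 | 0.158 | 66.1% | 932 |
| 50% | 0.072 | 0.132 | 57.3% | 1,144 |
| 40% | 0.058 | 0.106 | 47.4% | 1,462 |

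If men who cannot be offered PrEP were instead removed from the denominator, power would be 86.2% at g = 90% and 82.0% at g = 80%.

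**Step 3: the other Table 3 scenarios, at g = 80%.**

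| HIV-negative | Test uptake | Power at g = 100% | Power at g = 80% |
|---|---|---|---|
| 60% | 20% vs 55% | 99.9% | 99.1% |
| 60% | 20% vs 65% | >99.9% | >99.9% |
| 60% | 30% vs 55% | 89.5% | 80.1% |
| 60% | 30% vs 65% | 99.3% | 96.9% |
| 70% | 20% vs 55% | >99.9% | 99.7% |
| 70% | 20% vs 65% | >99.9% | >99.9% |
| 70% | 30% vs 55% | 94.4% | 86.9% |
| 70% | 30% vs 65% | 99.8% | 98.8% |

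With 20% excluded, six of the eight rows keep at least 96% power and a seventh keeps 87%. The scenario in the plan's power sentence is the one with no reserve.

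**The case against.** **The six-month wording may set how long PrEP lasts, not who may start.** This is a fair reading of the Aim 1 sentence, and no section says that a late tester is refused. The dispensing section makes the offer depend on the man's wish and the absence of acute HIV symptoms, under national guidelines. But a period that runs from the woman's ART start, as in Benefits, leaves nothing to offer a man who tests after it ends. The wording still bears on who can start, and it still conflicts with the other rules.

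**Few men may be affected.** Aim 1 speaks of women initiating PMTCT B+, and Recruitment describes immediate ART for women who test positive. If nearly all women start ART at about enrolment, few men are excluded because of earlier ART. This stands, and it is why g is shown as a range. A reader might infer that many men are shut out and that the power claim fails; the documents give no share that would support either statement.

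**The 80% may already allow for some exclusion.** The earlier demonstration project saw 97% uptake, and 80/97 is about 82%. If that was the intention, the loss begins only below an offered share of about 82%. The protocol does not say so; it presents 80% as uptake in HIV-negative men.

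**The power sentence is not an arithmetic error.** A reader using a pooled-variance formula would get 86.1% and might conclude that it is. That formula does not reproduce Table 3; the unpooled one does.

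**Late testing alone.** A reader might also assume that all women start ART at randomisation, that testing has a constant hazard giving 30% or 55% at one year, and that follow-up is 1 to 1.5 years as in SAP 3.2.1. From (1−e^(−h/2))/(1−e^(−hT)), with h = −ln(1−p), only 39% to 60% of eventual testers would come within six months. That does not carry over to the protocol's outcome: under the same assumption the offer window and both protocol outcome windows coincide, so a later tester is not a protocol event under any rule. Nor does Table 3 define its uptakes as one-year figures. The point concerns only the SAP's end-of-study analyses.

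**The SAP covers part of this.** SAP 2.2.1 (Aims 1b and 1c) and 5.2.2 include definitions that count an HIV-negative man as covered if his partner is suppressed, and SAP 7.2 plans subgroups by baseline suppression and prior ARVs. These help interpretation. They do not change the SAP 7.3.3 comparison, which counts men who start PrEP.

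**Conclusion.** The concern holds as a contradiction on a co-primary outcome together with an unstated condition on the power. The five offer rules cannot all apply, and neither can the three outcome windows. Because eligibility admits women already on ART, the window that runs from ART start can be closed at randomisation for some couples.

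The stated power is correct on its own inputs at 89.5%. In that scenario (60% HIV-negative, 30% vs 55% testing) it drops to 85.4% if an assumed 10% of HIV-negative testers cannot be offered PrEP, to 80.1% at 20% and to 57.3% at 50%. This assumes the same share in both arms and non-offered men counted as non-initiators. The true share is unknown from the documents and could be small. Most other Table 3 scenarios tolerate moderate exclusion. The point calls for reconciliation and a stated range; it does not show that the trial is underpowered.

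**What to change.** 1. Reconcile the protocol Summary, Specific Aims, Overall design, Objectives (Aim 1), Male partner procedures, PrEP medication and dispensation, Benefits, Table 6, the SAP Protocol Summary and SAP 3.4.1 into one statement of which HIV-negative men are offered PrEP. The choice of rule belongs to the clinical team.
2. Use one PrEP outcome window in Overall design, Outcome measurements, Statistical considerations and SAP 7.3.3. It should not be closed before randomisation for women already on ART.
3. State the power in the protocol's Sample size section and in SAP 3.2.1 as conditional on the offered share, with the range in the working. SAP 3.2.1 also repeats the power sentence beside a table listing 1,096 women for 90% power in the same scenario; that is a separate discrepancy, but it sits in the text being edited.
4. Record whether PrEP was offered (yes/no, with reason) and report it by arm beside initiation, so that not offered can be told from declined.

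Leave the SAP 7.3.3 denominators (enrolled HIV-negative men, and the estimated number of all HIV-negative partners) as they are; changing them would change the estimand.

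Cost: wording in both documents, one CRF field and a less favourable stated power. No extra participants.
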